5.2.4.2 Sensitivity and supplementary analyses

The primary efficacy analysis will be repeated on the PP set as a supplementary analysis (Statistical tables 14.2.2.1.1 to 14.2.2.2.1).

It will be also repeated on the FAS population excluding patients with unblinding issue (see section 5.3.6) (Statistical tables 14.2.3.1.1 to 14.2.3.1.3 & 14.2.3.2.1 to 14.2.3.2.2.).

Then, the primary efficacy analysis will be repeated on the FAS for patients IFN-K treated with status of IFN α neutralizing antibodies (positive/negative) at Week 36 as dependent variable.

(Statistical tables 14.2.3.3.1 & 14.2.3.3.2).

Finally, the following analysis will be presented as a sensitivity analysis.

The time variation in IFN gene signature (first co-primary endpoint) will be modelled using a MMRM (mixed model for repeated measures) with random intercept, with percent change at each time point as dependent variable, and minimization factors used for randomization (Ethnic origin (see section 9 Derived data), Age group, Presence or absence of renal involvement according to BILAG at screening, corticosteroid treatment, hydroxychloroquine treatment and MMF treatment at screening, treatment and time as explanatory variables.

The treatment by time interaction will also be included in the model. (Statistical table 14.2.4).

Linearity will be checked graphically. In case of absence of evidence of non-linearity, time will be treated as continuous (variable calculated as the actual number of days since baseline). Otherwise, it will be treated as categorical. (Statistical figure 14.2.1)

Statistical Analysis Plan

Study Name: IFN-K-002

SAP version & date: v4, 18/Jun/2018

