5.2.4 Efficacy analyses

5.2.4.1 Primary efficacy analysis

Descriptive statistics for IFN gene signature (first co-primary endpoint) at each visit and % of change from baseline by treatment group will be presented (Statistical tables 14.2.1.1.1 and 14.1.1.2).

The first co-primary efficacy endpoint - Percent of change from baseline after 36 weeks of treatment in the expression of IFN-induced genes – will be analyzed using an ANCOVA model (Statistical table 14.2.1.1.3).

The dependent variable will be the percentage of change from baseline in the expression of IFN-induced genes with the treatment as independent variable. The minimization factors used for randomization – Ethnic origin (see section 9 Derived data), Age group, Presence or absence of renal involvement according to BILAG at screening, corticosteroid treatment, hydroxychloroquine treatment and MMF treatment at screening - will be included as covariates. See section 5.3.2 for handling of missing data.

All IFN gene signature data will be listed in Listing 16.2.6.1.1.

Descriptive statistics for the response to treatment according to BICLA (second co-primary efficacy endpoint) at Week 36 will be presented by treatment group (Statistical table 14.2.1.2.1)

The second co-primary efficacy endpoint - response to treatment according to BICLA - will be analyzed using a logistic regression with the response rate as dependent variable and treatment as independent variable, while adjusting for the minimization factors used for randomization, as listed for the analysis of the first primary end-point (Statistical table 14.2.1.2.2).

Statistical Analysis Plan

Study Name: IFN-K-002

SAP version & date: v4, 18/Jun/2018

Response to treatment according to BICLA will be listed in Listing 16.2.6.1.2

First, the hypothesis with respect to the change from baseline in the expression of IFN-induced genes will be tested at an error probability of 5% for a 2-sided test. If and only if this Null-hypothesis can be rejected, the hypothesis with respect to the response to treatment according to BICLA will be tested also at an error probability of 5% for a 2-sided test.

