5.2.4.3 Secondary efficacy analyses

Secondary efficacy analyses will be performed on the FAS population except if otherwise specified.

5.2.4.3.1 *SRI response*

The SRI-4, 6, 8, 10 responses will be described at Week 36. (Statistical tables 14.2.5.1, 14.2.5.4, 14.2.6.1, 14.2.7.1, 14.2.8.1)

The SRI-4 response (section 4.1.2.1) will be analyzed using the same method as the primary analysis for the second co-primary endpoint (logistic regression). This analysis will be performed both on the FAS and PP sets. (Statistical tables 14.2.5.2 & 14.2.5.5)

The model on FAS for patients IFN-K treated with the status of IFN α neutralizing antibodies (positive/negative) at Week 36 as dependent variable will be also presented (Statistical table 14.2.5.3).

The SRI-6, 8, 10 responses to treatment at week 36 will also be analyzed using a logistic regression using the response rate as dependent variable and treatment as independent variable, while adjusting for the minimization factors used for randomization. (Statistical tables 14.2.6.2, 14.2.7.2, 14.2.8.2)

All analyses performed on SRI-4 will also be conducted on the composite SRI-4 (both with tapering CS \leq 5 mg and \leq 7.5 mg) on the FAS population only. (Statistical tables 14.2.5.6 to 14.2.5.11)

The SRI-4 response is an important and alternative endpoint assessing the clinical response. In case, there will be no trend on the BICLA response, the SRI-4 response could be chosen as primary endpoint for further development of IFN-K.

5.2.4.3.2 *SLEDAI response*

Number of patients achieving a SLEDAI response, defined as a reduction of the SLEDAI-2K score of at least 4 points at Week 36 compared to baseline will be analyzed using frequency table methods (Statistical table 14.2.9).

SLEDAI-2K score at each visit and change from baseline by treatment group will also be presented (Statistical tables 14.2.10.1 to 14.2.10.2).

All SLEDAI data will be listed in Listing 16.2.6.2.

5.2.4.3.3 *BILAG*

Shift tables between Baseline and LVA (last available value between Week 36 and Week 24) will also be presented for each body system. (Statistical table 14.2.11)

Finally, descriptive statistics for the BILAG global score at each visit and change from baseline to LVA will be presented. The difference between treatment groups for the change from baseline to LVA will be analyzed using the non-parametric Wilcoxon-test. (Statistical table 14.2.12)

Statistical Analysis Plan

Study Name: IFN-K-002

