5.2.5.2 Adverse events

Adverse event tabulations:

Tabulation of adverse events will present for each cell the following information: number of patients with at least one occurrence of the event, corresponding percentage and number of events (if relevant).

The following tables will be produced for the Safety population as well as by treatment group:

The definition of TEAEs is described in section 4.2.1.

The following period will be defined:

- before first dose
- [1st dose; 2nd dose[
- [2nd dose; 3rd dose[
- [3rd dose; 4th dose[
- [4th dose; 5th dose[
- [5th dose; Week 36]
- [Last dose; Week 36/Early Termination] (for AE which cannot be classified in the previous periods due to dose not received or premature study termination)

Summary table of adverse events (Statistical Table 14.3.2):

- Any AE
- Any TEAE
- Any TEAE by period
- Any TEAE leading to study treatment temporarily discontinuation
- Any TEAE leading to study treatment permanent discontinuation
- Any TEAE of intensity severe or more
- Any TEAE considered related to the study treatment (possibly or probably related)
- Any SAE
- Any SAE by period
- Any Treatment Emergent SAE (TESAE)
- Any TESAE leading to study treatment temporarily discontinuation
- Any TESAE leading to study treatment permanent discontinuation
- Any TESAE considered related to the study treatment (possibly or probably related)
- Any TESAE of intensity severe or more

Statistical Analysis Plan

Study Name: IFN-K-002

SAP version & date: v4, 18/Jun/2018

- Death

Detailed Tables:

All tables listed below will be presented by period (except if otherwise specified):

- Solicited local reactions during a 7-day follow-up period after each study product administration by SOC and PT (Statistical Tables 14.3.3.1 to 14.3.3.6)
- Solicited local reactions during a 7-day follow-up period after each study product administration by SOC, PT and intensity (Statistical Tables 14.3.4.1 to 14.3.4.6)
- Solicited systemic reactions during a 7-day follow-up period after each study product administration by SOC and PT (Statistical Tables 14.3.5.1 to 14.3.5.6)
- Solicited systemic reactions during a 7-day follow-up period after each study product administration by SOC, PT and intensity (Statistical Tables 14.3.6.1 to 14.3.6.6)
- TEAEs by SOC and PT (Statistical Tables 14.3.7.1 to 14.3.7.6)

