- TEAEs by SOC, PT and status of IFN α neutralizing antibodies (positive/negative) at time of event (only on patients IFN-K treated) (Statistical Tables 14.3.7.7 to 14.3.7.10)
- TEAEs by SOC, PT and relationship (Statistical Tables 14.3.8.1 to 14.3.8.6)
- TEAEs by SOC, PT and intensity (Statistical Tables 14.3.9.1 to 14.3.9.6)
- TEAEs leading to permanent study treatment discontinuation by SOC and PT (Statistical Table 14.3.10) (only throughout the study)
- SAEs by SOC and PT (Statistical Tables 14.3.11.1 to 14.3.11.7)
- SAEs by SOC, PT and status of IFN α neutralizing antibodies (positive/negative) at time of event (only on patients IFN-K treated) (Statistical Tables 14.3.11.8 to 14.3.11.11)
- SAEs by SOC, PT and relationship (Statistical Tables 14.3.12.1 to 14.3.12.7)
- SAEs by SOC, PT and intensity (Statistical Tables 14.3.13.1 to 14.3.13.7)
- SAEs leading to permanent study treatment discontinuation by SOC and PT (Statistical Table 14.3.14)

The following rules will be applied to analyze the occurrence of AE according to the status of IFN α neutralizing antibodies (positive/negative):

- For adverse event which occurred between dose 1 and dose 3 included, status of neutralizing capacity will not be assessed
- For adverse event which occurred between 3rd dose (excluded) and Visit 6 (included), status of neutralizing capacity at visit 6 will be used
- For adverse event which occurred between Visit 6 (excluded) and Visit 9 (included), status of neutralizing capacity at visit 9 will be used
- For adverse event which occurred between Visit 9 (excluded) and Visit 12 (included), status of neutralizing capacity at visit 12 will be used

Statistical Analysis Plan

Study Name: IFN-K-002

SAP version & date: v4, 18/Jun/2018

Statistical Analysis Plan

Study Name: IFN-K-002

SAP version & date: v4, 18/Jun/2018

Adverse events listings:

All adverse events (including solicited local and systemic reactions) recorded during the study will be presented in Listings. The following information (if available) will be included in the listings (non-exhaustive list):

- Patient identifier
- Age, Ethnic origin (see section 9 Derived data), gender, weight
- The adverse event (System organ class, preferred term, reported term)
- Start date, end date, duration, period
- Severity (e.g., mild, moderate, severe)
- Seriousness (serious/non-serious)
- Action taken
- Outcome
- Relatedness assessment

Listings will be provided for:

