14.2.3.1.2	Primary efficacy analysis - First co-primary endpoint - Change from baseline					X
14.2.3.1.3	Primary efficacy analysis - First co-primary endpoint - ANCOVA model					X
14.2.3.1.4	Primary efficacy analysis - First co-primary endpoint - ANCOVA model - Covariates as randomized			X		
14.2.3.2.1	Primary efficacy analysis - Second co-primary endpoint - Response at Week 36					X
14.2.3.2.2	Primary efficacy analysis - Second co-primary endpoint - Logistic regression model					X
14.2.3.2.3	Primary efficacy analysis - Second co-primary endpoint - Logistic regression model - Covariates as randomized			X		
14.2.3.3.1	Primary efficacy analysis - First co-primary endpoint - ANCOVA model with status of IFN α neutralizing antibodies (positive/negative) at Week 36 as dependent variable			X		

Statistical Analysis Plan

Study Name: IFN-K-002

SAP version & date: v4, 18/Jun/2018

Number	Title	Screened	SAF	FAS	PP	Other
14.2.3.3.2	Primary efficacy analysis - Second co-primary endpoint - Logistic regression model with status of IFN α neutralizing antibodies (positive/negative) at Week 36 as dependent variable			X		
14.2.4	Sensitivity efficacy analysis - First co-primary endpoint - MMRM			X		
14.2.5.1	Secondary efficacy analysis - SRI-4 response at Week 36			X		
14.2.5.2	Secondary efficacy analysis - SRI-4 response - Logistic regression model			X		
14.2.5.3	Secondary efficacy analysis - SRI-4 response - Logistic regression model with status of IFN α neutralizing antibodies (positive/negative) at Week 36 as dependent variable				X	
14.2.5.4	Secondary efficacy analysis - SRI-4 response at Week 36				X	
14.2.5.5	Secondary efficacy analysis - SRI-4 response - Logistic regression model				X	
14.2.5.6	Secondary efficacy analysis - Composite SRI-4 response (CS 5 mg) at Week 36			X		
14.2.5.7	Secondary efficacy analysis - Composite SRI-4 response (CS 5 mg) - Logistic regression model			X		
14.2.5.8	Secondary efficacy analysis - Composite SRI-4 response (CS 5 mg) - Logistic regression model with status of IFN α neutralizing antibodies (positive/negative) at Week 36 as dependent variable				X	
14.2.5.9	Secondary efficacy analysis - Composite SRI-4 response (CS 7.5 mg) at Week 36			X		
14.2.5.10	Secondary efficacy analysis - Composite SRI-4 response (CS 7.5 mg) - Logistic regression model			X		

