14.2.5.11	Secondary efficacy analysis - Composite SRI-4 response (CS 7.5 mg) - Logistic regression model with status of IFN α neutralizing antibodies (positive/negative) at Week 36 as dependent variable				X	
14.2.6.1	Secondary efficacy analysis - SRI-6 response at Week 36			X		
14.2.6.2	Secondary efficacy analysis - SRI-6 response at Week 36 - Logistic regression model			X		

Statistical Analysis Plan

Study Name: IFN-K-002

SAP version & date: v4, 18/Jun/2018

Number	Title	Screened	SAF	FAS	PP	Other
14.2.7.1	Secondary efficacy analysis - SRI-8 response at each visit			X		
14.2.7.2	Secondary efficacy analysis - SRI-8 response at Week 36 - Logistic regression model			X		
14.2.8.1	Secondary efficacy analysis - SRI-10 response at each visit			X		
14.2.8.2	Secondary efficacy analysis - SRI-10 response at Week 36 - Logistic regression model			X		
14.2.9	Secondary efficacy analysis - SLEDAI response at week 36			X		
14.2.10.1	Secondary efficacy analysis - SLEDAI-2K scores - Value at each visit			X		
14.2.10.2	Secondary efficacy analysis - SLEDAI-2K scores - Change from baseline			X		
14.2.11	Secondary efficacy analysis - BILAG - Shift table			X		
14.2.12	Secondary efficacy analysis - BILAG global score			X		
14.2.13	Secondary efficacy analysis - SELENA-SLEDAI - Mild, moderate or severe SLE flare			X		
14.2.14.1	Secondary efficacy analysis - SELENA-SLEDAI score - Value at each visit			X		
14.2.14.2	Secondary efficacy analysis - SELENA-SLEDAI score - Change from baseline			X		
14.2.15.1	Secondary efficacy analysis - SLICC/ACR-DI score - Value at each visit			X		
14.2.15.2	Secondary efficacy analysis - SLICC/ACR-DI score - Change from baseline			X		
14.2.16.1	Secondary efficacy analysis - CLASI - Total activity score - Value at each visit			X		
14.2.16.2	Secondary efficacy analysis - CLASI - Total activity score - Change from baseline			X		
14.2.17.1	Secondary efficacy analysis - CLASI - Total damage score - Value at each visit			X		
14.2.17.2	Secondary efficacy analysis - CLASI - Total damage score - Change from baseline			X		
14.2.18	Secondary efficacy analysis - LLDAS			X		
14.2.19	Immunogenicity analysis - Anti-IFN α binding antibody titers - Positive antibody response over time				X	
14.2.20	Immunogenicity analysis - Log-transformed dilution titers for anti-IFN α binding antibodies				X	

Statistical Analysis Plan

Study Name: IFN-K-002

SAP version & date: v4, 18/Jun/2018

Number	Title	Screened	SAF	FAS	PP	Other

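### The SAP makes Week 36 neutralizing-antibody status the outcome in five IFN-K-only models, where it should be the explanatory variable, and labels a closing-visit antibody status in the adverse event tables as status at the time of the event

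*SAP*

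**What the plan says.** **Models by antibody status.** SAP 5.2.4.1 sets the roles for the first co-primary model: "The dependent variable will be the percentage of change from baseline in the expression of IFN-induced genes with the treatment as independent variable". The BICLA logistic model in the same section is built alike, with response as dependent variable and treatment as independent variable.

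SAP 5.2.4.2 then repeats the primary analysis on the FAS in IFN-K-treated patients with "status of IFN α neutralizing antibodies (positive/negative) at Week 36 as dependent variable". SAP 5.2.4.3.1 describes an IFN-K-only SRI-4 model with status "positive/negative) at Week 36 as dependent variable will be also presented", and extends every SRI-4 analysis to the composite SRI-4 at both corticosteroid thresholds. The table list in SAP 10.1 agrees with the text. Title 14.2.3.3.1 reads in part "ANCOVA model with status of IFN α neutralizing antibodies (positive/negative) at Week 36 as dependent variable", and 14.2.5.11 reads in part "Composite SRI-4 response (CS 7.5 mg) - Logistic regression model with status of IFN α neutralizing antibodies (positive/negative) at Week 36 as dependent variable". Titles 14.2.3.3.2, 14.2.5.3 and 14.2.5.8 use the same wording.

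**Adverse events by antibody status.** SAP 5.2.5.2 announces TEAE and SAE tables by neutralizing status ("positive/negative) at time of event (only on patients IFN-K treated"). The rule below that list assigns the status found at the end of each interval, for example: "For adverse event which occurred between Visit 6 (excluded) and Visit 9 (included), status of neutralizing capacity at visit 9 will be used". Events from dose 1 to dose 3 get no status. Titles 14.3.7.7 to 14.3.7.10 add anti-IFNα binding status. The rule covers neutralizing status only.

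**Flares.** SAP 5.2.4.5.2 adjusts a second Cox model, in IFN-K patients, for presence or absence of neutralizing antibodies. It does not say at which visit.

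**The concern.** The five models are there to show whether IFN-K patients who develop neutralizing antibodies respond better than those who do not. That question needs the response on the left of the model and antibody status on the right. The SAP says the opposite in the text and in the table list, so a programmer working from either one gets the same instruction. Followed literally, five planned tables would not contain the intended estimate. One of them concerns SRI-4, which SAP 5.2.4.3.1 says could become the primary endpoint for further development.

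The adverse event label has a different effect. A reader of those tables would take the status shown as the status at onset, when it may have been measured weeks afterwards.

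**Working it through.** The SAP attaches no figure to this point, so there is none to reproduce. The check compares wording, counts places and reads intervals off the visit schedule.

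**1. Count of models.** Two co-primary models (5.2.4.2), one SRI-4 model and two composite SRI-4 models (5.2.4.3.1): 2 + 1 + 2 = 5. This matches the five titles. Places to correct: 2 sections + 5 titles = 7.

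**2. Variable roles side by side.**

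| | Outcome | Explanatory variable of interest | Patients |
|---|---|---|---|
| SAP 5.2.4.1, ANCOVA | percent change in IFN-gene expression | treatment | both arms |
| SAP 5.2.4.1, logistic | BICLA response | treatment | both arms |
| SAP 5.2.4.2 and 5.2.4.3.1, as written | antibody status | treatment, now constant | IFN-K only |
| SAP 5.2.4.5.2, second Cox model | time to flare | antibody status | IFN-K only |
| SAP 5.2.4.5.13, descriptions by status | clinical and biological parameters | antibody status | IFN-K, binding-positive, PP |

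The last two rows show how the SAP uses status elsewhere.

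**3. What a literal fit contains.** The minimization factors (SAP 2.3.1, 5.3.1) are ethnic origin in four categories (3 indicators) and five two-level factors: 3 + 5 = 8 columns. Adding an intercept and treatment gives 10 columns. Treatment equals the intercept column in IFN-K patients, so the rank is 9: treatment drops out, only the minimization factors remain as predictors, and the endpoint appears nowhere. With status in place of treatment and the endpoint as outcome, there are 10 columns of rank 10 and the contrast is estimable.

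**4. If the endpoint were moved to the right-hand side instead.** Two simulated data sets illustrate this. Each has 89 IFN-K patients and five two-level covariates. The difference of 32.6 points, the SD of 68 and the BICLA rates of 20.6% and 40.6% are borrowed from SAP 2.3.2. The positive shares are assumed.

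| Assumed share positive | Endpoint as outcome: points of IFN-gene change | Status as outcome: probability of being positive per point | p, both directions | BICLA odds ratio, endpoint as outcome / status as outcome |
|---|---|---|---|---|
| 30% | -28.5 | -0.0019 | 0.035 | 1.68 / 1.65 |
| 60% | -33.3 | -0.0012 | 0.064 | 5.56 / 5.51 |

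In the linear model the p-value is the same, but the estimate no longer means a difference in gene expression. In the logistic model the odds ratio hardly moves.

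**5. Adverse event intervals.** Nominal weeks come from the visit schedule.

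| Event falls in | Status taken from | Longest look-ahead | Mean if onset is uniform (assumed) |
|---|---|---|---|
| after dose 3 (Week 4) to Visit 6 (Week 12) | Visit 6 | 12 - 4 = 8 weeks | 4 weeks |
| after Visit 6 to Visit 9 (Week 24) | Visit 9 | 24 - 12 = 12 weeks | 6 weeks |
| after Visit 9 to Visit 12 (Week 36) | Visit 12 | 36 - 24 = 12 weeks | 6 weeks |

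The status is measured on or after the event in every case.

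**6. Titles affected by the label.** 14.3.7.7 to 14.3.7.10 (four) and 14.3.11.8 to 14.3.11.11 (four) make eight, plus two entries in the list in 5.2.5.2. Only the first four mention binding status.

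**The case against.** The best defence of the models is that the intention is plain. The sections speak of repeating the primary or SRI-4 analysis, the titles still name the endpoint, and the Cox model and the descriptions by status treat status as explanatory. The best defence of the adverse event tables is that the rule is spelled out directly beneath the list. Both arguments hold, and they keep the point minor. They do not remove it: the wrong role is stated consistently in seven places, and the label disagrees with the rule it stands over.

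A reader might infer more than the documents support:

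- *Patients who leave before a closing visit are not handled.* SAP 5.3.2 says no other missing data will be imputed, so an absent status stays missing. A period is also defined "for AE which cannot be classified in the previous periods due to dose not received or premature study termination".
- *The rule should use the last status before the event.* That gives the right time order but not better classification. In an illustration for Visits 6 to 9 (true rate ratio 2.0; share positive 0.3-0.7 at the opening visit and 0.8-0.9 at the closing visit; a sample at day 28; all assumed), the present rule reads 1.67-1.94 and the last-prior rule 1.55-1.82. It would also leave Weeks 4 to 12 without a post-dose neutralizing status, since the first such sample is at Visit 6.
- *The schedule contradicts itself on a Visit 11 neutralizing sample.* Both schedule tables appear to mark one and Protocol 10.9.11 lists none. Marks in neighbouring rows shift between the Visit 11 and 12 columns from one copy of the table to the other, so the tick cannot be relied on.
- *The flare Cox model is biased in favour of antibody-positive patients.* That depends on how status is defined, and the SAP gives no definition. Other IFN-K-only efficacy analyses by status use Week 36 (Visit 12). What is established is a missing date.

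**Conclusion.** The point holds and is minor. As written, five IFN-K-only models have the wrong outcome variable and would not estimate response by antibody status. This rests on wording alone, and a slip for *independent* is by far the likeliest explanation. The label on the adverse event tables contradicts their rule by nominally up to 8 weeks (dose 3 to Visit 6) or 12 weeks (the two later intervals). Binding status in four titles has no rule, and the Cox covariate has no date.

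The co-primary tests and the criterion for a positive study do not use any of these analyses. All are single-arm, non-randomized associations. Bias from a status measured after an event is possible, but the documents do not establish it or allow it to be sized.

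**What to change.** - In SAP 5.2.4.2, 5.2.4.3.1 and titles 14.2.3.3.1, 14.2.3.3.2, 14.2.5.3, 14.2.5.8 and 14.2.5.11, state that Week 36 neutralizing status is the independent variable in place of treatment. IFN-gene percent change, BICLA, SRI-4 or composite SRI-4 is the dependent variable, with the minimization factors as covariates. Label the results as exploratory, non-randomized associations.
- Retitle the adverse event tables by antibody status as *status at the next scheduled visit (6, 9 or 12)*, in SAP 5.2.5.2 and in titles 14.3.7.7 to 14.3.7.10 and 14.3.11.8 to 14.3.11.11. The rule itself can stay.
- Remove binding status from titles 14.3.7.7 to 14.3.7.10, or add a rule for it.
- State in SAP 5.2.4.5.2 the date or visit of the status used in the second Cox model.

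The cost is an edit to the SAP and table shells before database lock, plus a little programming if a binding rule is added. No new samples or visits are needed.
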